4.3 Screen Failures and Registered Participants Who Do Not begin Study Treatment

The DCC is to be notified of all participants who sign consent but do not meet eligibility criteria or do not initiate protocol therapy.

5.0 TREATMENT PROGRAM

5.1 Treatment Program Overview

This is a single-center open-label, Phase 2 clinical trial of radium Ra 223 dichloride in combination with standard of care androgen deprivation therapy (ADT) and stereotactic body radiation therapy (SBRT) for participants with metastatic castration sensitive prostate cancer ([Section 5.3](#)).

Treatment will be administered in an outpatient basis.

SBRT and radium Ra 223 dichloride will be administered in 28 day treatment cycles ([Section 5.2](#)). Up to 7 cycles of protocol therapy is planned in the absence of unacceptable toxicity or disease progression, whichever comes first. If one agent is discontinued due to toxicity, then the participant may continue to receive the other protocol therapy agent(s).

While the participant is on protocol therapy, they will receive bisphosphonate or RANKL inhibitor bone health agents at the dose and schedule consistent with the treatment of bone metastases or prevention of osteoporosis, until their testosterone levels are within the normal range (>50 ng/dL) or at the discretion of the PI.

Participants who end protocol therapy will undergo follow-up ([Section 5.9](#)). Windows for all assessments and treatments are detailed in [Section 11.0](#).

5.2 Cycle Definition

In the absence of delay due to toxicity, each treatment cycle lasts 28 days.

Cycle 1 Day 1 is defined by the administration of SBRT.

Cycles 2-7 Day 1 is defined by the administration of radium Ra 223 dichloride.

Post Ra-223 is defined as approximately 28 days post-last dose of radium Ra 223 dichloride.

5.3 Treatment Plan

The treatment plan is as follows ([Table 5.3](#)). Participants must already have received at least 28 days of ADT (leuprolide OR goserelin OR degarelix OR relugolix) **prior** to initiating Cycle 1 Day 1 SBRT. While on protocol therapy, participants must also receive bisphosphonate or RANKL inhibitor bone health agents at the dose and schedule consistent with the treatment of bone metastases or prevention of osteoporosis, until their testosterone levels reach the normal range or at the discretion of the PI.

Stopping rules may be implemented if there is unacceptable toxicity. For further details see [Section 13.0](#)

Table 5.3 Treatment Regimen and Schedule

Agent/Therapy and Route of Administration	Dose	Timing of administration and planned duration
Stereotactic Body Radiation Therapy (SBRT) via External Beam Radiation via TrueBeam Stx	9Gy x 3 fractions (bone) 5Gy x 5 fractions (lymph node) 10Gyx5 (lung)	Cycle 1 Day 1, then dosing administered minimum every 40 hours over 7 to 21 days during Cycle 1
Radium Ra 223 dichloride via Slow IV over 1 minute	55 kBq/kg	Cycles 2-7 Day 1 of each 28-day cycle
Leuprolide OR goserelin OR degarelix OR relugolix Per package insert/investigator discretion		Starting at least 4 weeks prior to SBRT and continuing for a total of 36 weeks as part of regimen on protocol

5.4 Agent Administration

5.4.1 Androgen deprivation therapy

Luteinizing hormone-releasing hormone (LHRH) agonists consisting of either leuprolide OR goserelin OR LHRH antagonist degarelix OR relugolix will be administered per package insert and investigator discretion.

Participants will receive in total 36 weeks of therapy with a LHRH agonist/antagonist; starting at least 28 days prior to initiating Cycle 1 Day 1 stereotactic body radiation therapy.

There is no requirement that the same LHRH agonist/antagonist (whether leuprolide or goserelin or degarelix or relugolix) be administered for the duration of the study.

Dose delay guidelines are described in [Section 6.3](#).

5.4.2 Stereotactic body radiation therapy (SBRT)

Participants **must meet criteria** in [Section 6.1](#) to initiate SBRT on Cycle 1 Day 1.

SBRT will be administered by a trained radiation oncologist. Radiation therapy will initiate at least 28 days following initiation of leuprolide OR goserelin OR degarelix OR relugolix. Participant dosing is described in [Table 5.3](#).

Participants will receive 3 or 5 fractions as determined by the location of the metastases to be irradiated during Cycle 1. There should be a minimum of 40 hours between treatments for an individual metastasis.

For supportive care guidelines refer to [Section 5.9](#).

For administration details refer to [Section 9.3](#). For dose modification refer to [Section 6.3](#).

5.4.3 Radium Ra 223 dichloride

Participants will receive 6 cycles of Radium Ra 223 dichloride following completion of SBRT.

Participants **must meet criteria** in [Section 6.2](#) to receive the **first dose** of radium Ra 223 dichloride.

Radium Ra 223 dichloride will be administered as a slow bolus intravenous injection over 1 minute by a trained physician.

The volume of radium Ra 223 dichloride to be administered to a given participant should be calculated using the:

- Participant's body weight (kg)- calculated **within 30 days** of the dosing day
- Dosage level 55kBq/kg body weight
- Radioactivity concentration of the product (1,100 kBq/mL; 30 microcurie/mL) at reference date
- Decay correction factor to correct for physical decay of Radium Ra 223 dichloride
 - Radium-223 is an alpha particle emitter with a physical t_{1/2} of 11.4 days.

$$\text{Volume to be administered (mL)} = \frac{\text{Body weight in kg} \times 55 \text{ kBq/kg body weight}}{\text{Decay factor} \times 1,100 \text{ kBq/mL}}$$

Before administration of radium Ra 223 dichloride, the participant must be well hydrated; the participant should be instructed to drink ad libitum.

For additional information regarding administration and preparation refer to [Section 9.1](#).

Prophylactic treatment for nausea and vomiting is not recommended. For supportive care guidelines refer to [Section 5.9](#).

For dose delays due to treatment-related toxicity refer to [Section 6.2](#).

5.5 Assessments and Special Monitoring

For a detailed list of all study procedures including timing and windows, see [Section 11.0](#).

Note: Protocol therapy should be administered on Day 1 of each cycle after all procedures/safety assessments have been completed.

It may be necessary to perform study procedures at unscheduled time points if deemed clinically necessary by the investigator.

5.5.1 Special Monitoring

Gastrointestinal AEs

- Radium Ra 223 dichloride increases AEs such as diarrhea, nausea, and vomiting, which may result in dehydration. Constipation has also been reported in participants receiving radium Ra 223 dichloride.
- Participants should be educated to report signs of dehydration, hypovolemia, urinary retention or renal insufficiency/failure.

Secondary Malignant Neoplasms

- Treatment with radium-223 dichloride contributes to a patient's overall long-term cumulative radiation exposure.
- Long-term cumulative radiation exposure may be associated with an increased risk of cancer and hereditary defects.
- Monitor for incidence of osteosarcoma or other secondary neoplasms.

5.6 Criteria for Removal from Protocol Therapy

Participants will receive protocol therapy until one of the following criteria are met:

- Disease progression despite castration levels of testosterone < 50 ng/dL
- Completion of 7 cycles of protocol therapy
- Participant is deemed intolerant to protocol therapy because of toxicity, despite dose modification/ delay
 - **Note:** Participants may continue to receive ADT as clinically indicated and per investigator discretion if the other study agents are discontinued.
- Withdrawal of consent for future protocol therapy (See [Section 17.5](#))
- General or specific changes in the participant's condition that render the participant unacceptable for further treatment in the opinion of the treating investigator.

Once participants meet criteria for removal from protocol therapy, the participant should then proceed to End of Treatment assessments.

Documentation of the reason for discontinuing protocol therapy and the date effective should be made in the Electronic Health Record (EHR) and appropriate eCRF.

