2.6 Overview and Rationale of Study Design

The SHARP study is a single-center open-label, Phase 2 clinical trial of stereotactic body radiation therapy (SBRT), hormone/androgen deprivation therapy (ADT) and radium Ra 223 dichloride for participants with newly diagnosed oligometastatic castration sensitive prostate cancer.

Eligibility

Participants will be adults diagnosed with metastatic prostate adenocarcinoma who have undergone full treatment at the primary prostate site. Participants will be chemotherapy naïve to metastatic sites, unless exposure occurred during treatment for primary disease.

Oligometastatic burden will be limited to a maximum of four lesions, consistent with a summary analysis demonstrating improved prognosis for SBRT in prostate cancer for participants with four or fewer lesions [22]. In addition, participants must have at least one bone lesion to increase benefit over any risk from the bone specific radium Ra 223 dichloride regimen.

Participants must have at least one bone lesion and each non-visceral lesion (bone and lymph node) should not exceed more than 5 cm. In addition, participants may have one lung lesion (< 2cm); no liver lesions are permitted.

Treatment program

The treatment program is comprised of SBRT, administered over the first cycle, radium Ra 223 dichloride administered over 6 cycles, and concurrent standard of care ADT (luteinizing hormone-releasing hormone agonist-either leuprolide or goserelin, or LHRH antagonist degarelix or relugolix). Each treatment cycle is 28 days.

Participants will be receiving ADT for approximately 36 weeks as part of this study (can be started prior to consent) to increase radiosensitivity [23, 41]. Metastatic prostate cancer patients often present at COH having initiated standard of care ADT. Therefore, there is no benefit derived from monitoring patients during their initial single-agent standard of care ADT.

Typically standard of care ADT is continued indefinitely however it is associated with side effects of fatigue, hot flushes, erectile dysfunction, muscle loss, osteoporosis and sometime “drug holidays” are given. Thus, ADT will be discontinued after a total of 36 weeks and participants will be monitored carefully. We hypothesize that some patients may achieve long-term remission off ADT, however upon disease recurrence ADT (and other appropriate standard treatment) will be resumed.

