- Note: patients with asymptomatic low volume locoregional recurrent disease will be allowed to enroll on this study after discussion with the PI. In the case where the low volume recurrence is amenable to SBRT, it will be included in the SBRT treatment. In the case where the low volume recurrence is not amenable to SBRT based on reirradiation risk, then we will follow these lesions with re-imaging scans and reassess at later time points for further local control. Additionally, if these patients fail only at the untreated site (due to the untreated recurrence/disease not being amenable to SBRT) they will be censored in the primary efficacy analysis at that time.

__12. Does not have castration resistant disease

- Castration resistance defined as progression of disease despite serum testosterone level of <50 ng/dL

__13. PSA \geq 0.2 prior to start of androgen deprivation treatment

PSA value:

Date:

__14. Patients will be receiving approximately 36 weeks of ADT as part of this trial. The 36 weeks of ADT may start prior to consenting to this study. The patient may join the study at any point of the 36-week period of ADT treatment.

- Only Luteinizing hormone-releasing hormone (LHRH) agonist/antagonist treatment is considered ADT; bicalutamide or other antiandrogens used alone do not count.

Patient MRN	Patient Initials (F, M, L):
-------------	-----------------------------

___15. Patients must be willing to receive bisphosphonate or RANKL inhibitor bone health agents at the dose and schedule consistent with the treatment of bone metastases or prevention of osteoporosis, starting approximately from when the patient begins protocol therapy, until the patient's testosterone reaches normal levels or at the discretion of the PI. Patients who are already on a bone health agent separate from the protocol may continue on this treatment regimen and will not be required to start treatment with an additional bone health agent.

___16. Patients may have received prior hormone therapy at the discretion of the PI. Patients may have received prior targeted therapy in the context of definitive therapy.

___17. Patients may have had one prior systemic non-chemotherapeutic treatment (i.e. immunotherapy, receptor tyrosine kinase inhibitor, antiangiogenic agent, differentiating agent) for recurrent or metastatic disease.

___18. Must have refused standard of care treatment for metastatic disease

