5.9.1 Prohibited Therapy

The following therapies are prohibited from **Cycle 1 Day 1 until completion of End of Treatment visit procedures**.

- Other investigational therapy/agent
- Other anticancer agents
- Antiandrogen agents (bicalutamide, flutamide)
- EXCEPTION: patients that enrolled on the study with asymptomatic low volume locoregional recurrent disease which was not amenable to SBRT at the time of enrollment will be followed with re-imaging scans. They will be reassessed at later time points during the study for further local control if needed.

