- e. *Cycle 1 Day 1*: With the exception of PSA, serum testosterone and blood counts other screening evaluations performed within 14 days prior to Cycle 1 Day 1 of protocol therapy may serve as Day 1 baseline evaluations.
- f. Participants must meet criteria in [Section 6.1](#) to initiate SBRT on Cycle 1 Day 1.
- g. Assessments must be performed **within 7 days** prior to radium Ra 223 dichloride. Safety assessments must be reviewed within 7 days prior to initiating a new cycle.
- h. *Cycle 2 Day 1 (1st dose of radium Ra 223 dichloride)*: Participants must meet criteria in [Section 6.2](#).
- i. *Post Ra-223/EOT visit to occur approx. 28 days +/- 7 days post-last dose of Ra 223 dichloride*.
- j. *Response follow-up* assessments for participants yet to progress, will occur ~ every 3 months (± 4 wks) (except [tumor evaluations](#)) from the day of last response evaluation until progression or the initiation of a new therapy.
- k. *Long-term follow-up* assessments for participants who progressed or ended Response Follow-up to occur annually (± 30 days) or as requested by the Study PI via medical record review, review of social security registry/ public records, and/or telephone call.
- l. *Informed consent* process to be fully documented (see [Section 17.4](#)). Informed consent must occur prior to any research only (non-SOC) screening procedures.
- m. *Medical history* to include a review of treatment history, any ongoing medical conditions and medical history pertaining to eligibility on study and involvement during study.
- n. *Eligibility criteria* are detailed in [Section 3.0](#).
- o. *Registration* into a COH clinical trial management system (CTMS).
- p. *Standard physical exam* includes weight and skin analysis.
- q. *Vital signs*: heart rate, blood pressure, respiration rate, and temperature.
- r. *Concurrent medications* and reason for administration to be documented in the EHR and eCRF from within 56 days prior to protocol therapy up to EOT visit. See [Section 5.11.1](#) for concomitant medication restrictions and guidelines.
- s. *Adverse event (AE)* will be assessed using CTCAE v.5.0.
- t. Active AE reporting will start from start of treatment until the post RA-223 visit/EOT visit **NOTE**: The highest AE grade per cycle will be reported in the eCRF from start of therapy until the EOT visit. **Exceptions to expedited reporting** are stated in [Section 8.2](#)

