12.0 ENDPOINT EVALUATION CRITERIA/MEASUREMENT OF EFFECT

12.1 Efficacy Endpoints

Response and progression will be evaluated in this study using modified Prostate Cancer Working Group 2 criteria [43] (see [Appendix C](#) and [Appendix D](#)). PSA levels will be a part of overall response assessment. Other clinical efficacy endpoints are described in [Table 12.1](#).

Table 12.1 Efficacy Endpoints

Endpoint	Definition
Time to treatment failure (TTF)	Time from the initiation of ADT for metastatic disease until PSA increase to > pre-ADT level or PSA >10 (whichever is smaller) or radiographic or clinical progression or resumption of ADT by physician's choice
Objective response rate (ORR)	Proportion of patients achieving CR or PR at Cycle 8 Day 1 (post-6 doses of radium Ra 223 dichloride)
Complete response (CR) rate	Proportion of patients achieving CR
Progression-free survival (PFS)	Time from the initiation of ADT for metastatic disease until PSA progression or radiographic progression or death
Bone specific progression-free survival (Bs-PFS)	Time to progression of bone specific disease over baseline
Duration of response (DOR)	Time from documented response to recurrent or progressive disease is first met
Duration of overall complete response	Time from documented CR to recurrent/ progressive disease
Duration of stable disease	Time from start of treatment until the criteria for progression are met, taking as reference the smallest measurements recorded since the treatment started.
Overall Survival (OS)	Date of initiation of protocol treatment to date of death from any cause

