13.5 Statistical Analysis Plan

With 24 evaluable patients treated we will estimate median time to treatment failure (radiographic or PSA progression, death or cessation of treatment due to clinical progression or toxicity). Our historical data suggest a 16 month median time to TTF [10]. Other studies varied in results and endpoints used, ranging from a median time to failure of 11 months [45], median distant progression free survival of 21 months [46], and median time to clinical progression of 18 months [23]. Even when permitting a lower PSA entry criteria ($PSA > 0.2$) the median time to progression was 21 months [14]. (Note: This observation has allowed us to amend this study to permit that lower PSA entry criteria to help with accrual). We seek to demonstrate a median TTF of at least 25 months, exceeding reports from all previous prior studies that examined only a two modality approach. With 24 evaluable patients, accrued over 16 months and followed for 18 months, we will have greater than 80% power to detect an improvement in TTF from 16 months to 32 months with a one-sided type I error of 10%. The critical value for a promising median TTF based on this design is 25 months, or an improvement of 9 months over our historical data. If patients experience treatment failure at ONLY an untreated asymptomatic low volume locoregional recurrence (allowed per amendment 6 based on PI discretion), TTF will be censored at that time for that patient.

Other secondary analysis will include progression-free survival, overall survival, complete response rate, duration of response, and duration of overall complete response, bone specific progression-free survival and duration of stable disease.

Exploratory analysis will include describing the rate of normalization of the total alkaline phosphatase level at the end of protocol therapy and evaluation of the role of genomic mutations and immune biomarker

studies on outcome and toxicity. These outcomes will be reported to provide further support, combined with the activity, and tolerability to help guide additional studies.

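### Starting a new anticancer therapy after the End of Treatment visit is not a TTF event under either definition, yet it ends PSA and scan assessment, which pushes median TTF upward

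*Combined protocol and SAP*

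**What the plan says.** **Two TTF definitions.**
- Table 12.1 starts the clock at ADT for metastatic disease. It counts a PSA above the pre-ADT level or above 10 (whichever is smaller), radiographic or clinical progression, and "resumption of ADT by physician's choice".
- Section 13.5 counts radiographic or PSA progression, death, and stopping treatment for clinical progression or toxicity. It does not mention ADT resumption.
- Neither lists the start of another anticancer therapy. The only TTF censoring rule is for failure solely at an untreated low-volume locoregional recurrence.

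**Therapy after treatment.** Section 5.9.1 bars other anticancer agents and anti-androgens from Cycle 1 Day 1 "until completion of End of Treatment visit procedures". Section 2.6 expects ADT, and other standard treatment as appropriate, at recurrence.

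**Assessment.** Study Calendar footnote j schedules response follow-up "from the day of last response evaluation until progression or the initiation of a new therapy". Section 5.7 then limits follow-up to survival and long-term toxicity, typically by record review.

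**ADT duration.** Section 2.6 says "ADT will be discontinued after a total of 36 weeks and participants will be monitored carefully", and Section 5.4.1 gives the same total. Section 5.6, under removal for toxicity, says "Participants may continue to receive ADT as clinically indicated and per investigator discretion if the other study agents are discontinued". Section 6.3 has a similar allowance when radium is discontinued. Neither allowance states a time limit.

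**What counts as ADT.** Inclusion criterion 14 says "bicalutamide or other antiandrogens used alone do not count". Appendix C, when defining baseline PSA, includes an anti-androgen within ADT.

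**Medication records.** Footnote r requires concurrent medications "to be documented in the EHR and eCRF from within 56 days prior to protocol therapy up to EOT visit". The calendar grid also marks them in Response Follow-up.

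**The concern.** In this design ADT is stopped and the time to failure is then observed. A man whose PSA is climbing but still below the Table 12.1 threshold may be started on another agent once the prohibition has lapsed. That start is not an event, and it ends the PSA and scan schedule that would have recorded one. No rule says whether he is an event, censored, or followed on. An analyst who censors him at his last assessment removes him just as he is failing. That is informative censoring, and it lengthens median TTF.

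The trial has 24 evaluable men, one arm, and a decision value of 25 months set against a historical 16. A few men handled this way can change the conclusion. The two conflicting definitions, the two meanings of ADT and the two medication-capture periods make it harder to settle these cases afterwards.

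**Working it through.** **1. When the prohibition lapses.** If ADT starts 28 days before Cycle 1 Day 1, the seventh cycle starts on day 28 + 6 x 28 = 196. The End of Treatment visit, 28 days later, falls on day 224, which is week 32. ADT is planned to week 36. On that schedule the bar on other agents ends about four weeks before ADT does, and so before the period in which most failures are expected. Men who started ADT earlier reach the visit later in their ADT course.

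**2. The plan's own figure.** Section 13.5 states "With 24 evaluable patients, accrued over 16 months and followed for 18 months", a median of 16 versus 32 months, one-sided error 10% and power above 80%. With exponential times, lambda = ln2/m, accrual A = 16 and further follow-up F = 18:

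p(m) = 1 - [exp(-lambda F) - exp(-lambda(A+F))]/(lambda A)

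- m = 16: p = 0.669, or 16.1 events in 24 men.
- m = 32: p = 0.428, or 10.3 events.
- Log-hazard test using the 10.3 events: power = Phi(sqrt(10.27) x ln2 - 1.2816) = Phi(0.939) = 0.826.
- One-sample log-rank, simulated: 0.88 to 0.90.

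The stated power reproduces.

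**3. The 25-month rule with no off-plan therapy.** By simulation, the chance of an observed median of 25 months or more at a true 16 is 0.046 (exponential estimate) or 0.051 (Kaplan-Meier). At a true 32 it is 0.80 or 0.76.

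**4. Censoring at new therapy.** Assumption: a random share f of men start new therapy 0 to 3 months before they would have failed. The documents supply neither number. The true median is 16 months, with 100,000 runs per setting.

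| Share f | Censored: exponential | Censored: Kaplan-Meier | Counted as event (both methods) |
|---|---|---|---|
| 0 | 0.046 | 0.051-0.052 | same |
| 10% | 0.104-0.111 | 0.123-0.132 | 0.042-0.052 |
| 20% | 0.195-0.219 | 0.221-0.244 | 0.035-0.052 |

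With new therapy counted as an event, power at a true 32 months is 0.77-0.80 (exponential) or 0.74-0.77 (Kaplan-Meier) for these shares.

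Section 13.3 now expects 66 months of accrual. The same simulation with A = 66 and F = 18 starts lower, at 0.02 (exponential) and 0.04 (Kaplan-Meier). It gives 0.06-0.11 for f = 10% and 0.16-0.23 for f = 20%. The pattern is the same, but the 10% share then sits around the planned error rather than clearly above it.

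**5. Follow-up continued, new therapy ignored.** If assessment went on and new therapy only delayed the listed event, 25% of men delayed by 6 months gives 0.09, and by 9 months 0.12. This route is weaker than censoring.

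**6. Continued ADT.** Section 2.2 gives 14 to 30 months to progression on continued ADT. For 6 of 24 men on it and the rest at 16 months, solve (6/24) x 0.5^(t/m) + (18/24) x 0.5^(t/16) = 0.5. The apparent median is 15.5 months (m = 14), 17.3 (m = 22) or 18.5 (m = 30).

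**The case against.** Several points on the other side stand.

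- **No rule actually censors at new therapy.** True. The gap is that nothing is specified. Censoring at the last assessment is the natural default when scheduled PSA and scans have ended.
- **Some of these men may count anyway.** A physician might record clinical progression, and Appendix C would let an anti-androgen qualify as ADT resumption under Table 12.1. But TTF has no criteria for clinical progression, and inclusion criterion 14 points the other way on anti-androgens.
- **The share affected is unknown**, and the documents do not say how the historical 16 months treated later therapy. Both are correct, so the size is illustrative and the net bias against that figure cannot be computed.

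Three stronger readings are tempting but not supported.

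- **That six men kept on ADT would reach the 25-month target with no regimen effect.** This needs all six never to fail: 0.25 + 0.75 x 0.5^(t/16) = 0.5 gives t = 16 x log2(3) = 25.4. Section 2.2 says men on continued ADT do progress, and its range gives 15.5 to 18.5 months. Even at 30 months, 18 of the 24 would have to be on continued ADT to pass 25.
- **That men on continued ADT escape failure.** Continued ADT is not a new therapy, so footnote j keeps them in PSA, testosterone and scan follow-up. Section 13.5 may already count those who stopped for toxicity as failures. Sections 5.6 and 6.3 can also be read as allowing only completion of the planned course.
- **That off-plan therapy goes unrecorded.** The grid marks concurrent medications, and testosterone, in Response Follow-up. The finding is a conflict with footnote r. Table 14.3 does, however, list no dedicated form for subsequent anticancer therapy.

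**Conclusion.** The point holds for new anticancer therapy started after the End of Treatment visit. It is a TTF event under neither definition, it ends PSA and scan assessment, and no rule says how to count the man. The likely effect is a longer median TTF. Under exponential failure times, the Section 13.5 accrual and follow-up, and the assumed 10-20% of men censored 0 to 3 months before failure, the false-positive chance of the 25-month rule goes from about 0.05 to 0.10-0.24. Counting new therapy as an event holds it at about 0.04-0.05.

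The conflicts over TTF components, over whether an anti-androgen alone is ADT, and over the end of medication capture follow from the text and need no assumption. Continued ADT is a lesser matter: its duration and its handling in the analysis need stating, but its effect on the median is modest on the protocol's own figures.

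**What to change.** 1. Put one TTF definition in Table 12.1 and Section 13.5, settling whether ADT resumption, death and stopping for toxicity count. In it, count the start of any non-protocol anticancer therapy, including an anti-androgen alone, as an event on its start date. Keep the stated censoring and the local-control exception for untreated locoregional recurrence. Add a sensitivity analysis that censors at the therapy start date.
2. Report men who stay on ADT past the planned stop in a sensitivity analysis, as an event or censored at that point. Counting them as failures in the main analysis is debatable, because they may not have progressed. Reconcile Sections 2.6 and 5.4.1 with Sections 5.6 and 6.3 on ADT duration; which clinical rule applies is for the investigators.
3. Use one meaning of ADT for endpoint purposes, reconciling inclusion criterion 14 with Appendix C.
4. Align footnote r with the calendar grid, and record the dates of ADT stop, ADT restart and every new anticancer therapy through follow-up.
5. Amend footnote j so that standard-of-care PSA and scan results are still abstracted after new therapy, for PFS and bone-specific PFS.

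The cost is wording and a few eCRF fields, filled largely from record review already planned. Median TTF may come out slightly less favourable. No treatment decision changes.
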